For patients who do not require washout, baseline will be the last visit of the originating study. Patients who received oral systemic AD treatment as rescue therapy during the originating study require a 4-week washout and will have an additional screening visit in Study JAHN (Visit 1 [Week 0]). The assessments collected at this visit will provide the Study JAHN baseline for these patients. If labs were not collected at this visit, then the most recent lab value collected at the last visit of the originating study will be used as baseline.

Period 2

For analysis of endpoints assessed at scheduled visits in Period 2, baseline from originating study will be used for categorical endpoints, such as EASI75, Itch NRS ≥ 4 -point improvement response, etc. Baseline from originating study will also be used for EASI-related, continuous endpoints, such as EASI change or percent change from baseline. For the other continuous endpoints such as Itch NRS and DLQI change from baseline, the analysis will be done using the Week 52 baseline. The methodology for defining Week 52 as the baseline is the same as the methodology for defining Week 0 of the originating study described above, anchoring on the first study drug administration of Period 2.

Safety Analyses

Safety analyses for treatment Period 1, and for Treatment Periods 1 and 2 combined (box plots of laboratory analytes and vital signs) will be conducted using the Study JAHN baseline, which is defined as the last nonmissing scheduled (planned) measurement on or prior to the date of first study drug administration for continuous measures by-visit analyses and non-missing measurements on or prior to the date of first study drug administration in Study JAHN for all other analyses. Safety analyses for Treatment Period 2 will be conducted for AEs only. Baseline for Treatment Period 2 is defined as nonmissing measurements on or prior to the date of first study drug administration in Treatment Period 2 of Study JAHN.

Postbaseline

Period 1(Weeks 0 to 52)

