For nonresponders, the main analysis method for all continuous efficacy variables will use MMRM analysis. The MMRM model will use a restricted maximum likelihood estimation. The model will include treatment, region, baseline disease severity (IGA), visit, and treatment-by-visit interaction as fixed categorical effects, and baseline and baseline-by-visit interaction as fixed continuous effects. For daily diary assessment endpoints, the model term 'visit' will include each of 16 weeks. An unstructured (co)variance structure will be used to model the between- and within-patient errors. If this analysis fails to converge, the heterogeneous autoregressive (ARH[1]), followed by the heterogeneous compound symmetry (CSH), followed by the heterogeneous Toeplitz, followed by autoregressive (AR[1]), followed by compound symmetry will be used. The Kenward-Roger method will be used to estimate the degrees of freedom. Treatment least square means (LSM) will be estimated within the framework of the MMRM using type 3 sums of squares. Differences in LSM between each dose of baricitinib and an appropriate comparator (and associated p-values, standard errors and 95% CI) will be used for statistical inference. The LSM difference, standard error, p-value, and 95% CI will be reported. For responders and partial responders, descriptive statistics will be provided for all continuous efficacy and health outcomes variables.

Treatment comparisons for select continuous efficacy and health outcomes variables may also be made using ANCOVA for primary and secondary objectives. For Period 1 analysis, when an ANCOVA model is used, the model includes region, baseline disease severity, treatment group, and baseline value. Treatment LSM will be estimated within the framework of the ANCOVA using type 3 sums of squares. Reported differences in LSM and associated p-values, standard errors, and 95% CI will be used for statistical inference. Analysis of covariance will be the primary method of analysis for continuous efficacy and health outcome variables for Period 2. In this Period, ANCOVA model includes region, baseline disease severity at Week 52, treatment group, and baseline value at Week 52. Baseline disease severity is defined previously.

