 - If year of onset is missing, duration of AD will be set as missing. Otherwise, unknown month will be taken as January, and unknown day will be taken as 01. The duration of AD will be rounded to 1 decimal place.
- duration of AD (years) category (0 to <2 years, 2 to <5 years, 5 to <10 years, 10 to <20 years, ≥20 years)
- diagnosis age (year), derived using diagnosis date as the reference start date and July 1st of birth year and truncated to a whole-integer age
- diagnosis age group (<18, ≥18 to <50, ≥50 years old)
- change from baseline = postbaseline measurement at Visit x – baseline measurement from originating study
 - If a baseline value is missing, it will not be imputed and the change from baseline will not be calculated.
- percent change from baseline at Visit x:

$$([\text{postbaseline measurement at Visit x} - \text{baseline measurement}] / \text{baseline measurement}) * 100$$
 - If a baseline value is missing, it will not be imputed and percent change from baseline will not be calculated.
- Weight (kg) = weight (lbs) * 0.454
- Weight category (<60 kg, ≥60 to <100 kg, ≥100 kg)
- Height (cm) = height (in) * 2.54
- cyclosporine inadequate efficacy prior to entry into originating study (yes, no)
 - Set to **yes** if the reason for discontinuation is inadequate response.

- cyclosporine intolerance prior to entry into originating study (yes, no)
 - Set to **yes** if the reasons for discontinuation are: intolerance to medication or contraindication (physician indicated cyclosporine was used and a contraindication was noted).
- cyclosporine contraindication (ineligible) prior to entry into originating study (yes, no)
 - Set to **yes** if cyclosporine was never used because of a contraindication.
- cyclosporine inadvisable prior to entry into originating study (yes, no)
 - Set to **yes** if the following reasons were selected for either not using the medication or discontinuing the medication:
 - reason for not using medication: physician decision, concern about side effects, unfavorable benefit risk, contraindication.
 - reasons for discontinuation: inadequate response, intolerance to medication, or contraindication.
- TCNI inadequate efficacy prior to entry into originating study (yes, no)
 - Set to **yes** if the reason for discontinuation is inadequate response.
- TCNI intolerance prior to entry into originating study (yes, no)

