6.3. Adjustments for Covariates

The randomization to treatment groups in the originating studies is stratified by disease severity (IGA) and geographic region. For Period 1, the covariates used in the logistic model for categorical data will include the baseline value from the originating study. When an MMRM analysis is performed, baseline value from originating study and baseline-by-visit interactions will be included as covariates. Unless otherwise specified, the statistical analysis models will adjust for these stratification variables. For Period 2, the covariates used in the logistic model for categorical data will include the baseline value from Week 52.

The baseline value from Study JAHN will be used as a covariate in the ANCOVA model for continuous safety data.

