		Randomized Downtitration Withdrawal Substudy Population with Week 52 IGA of 0 or 1			Secondary for mLOCF Sensitivity for NRI
		Period 2 non-study population Open-label Period 2 non-study population	Descriptive using observed, NRI and mLOCF	Week 52-200	Secondary, exploratory Secondary for mLOCF Sensitivity for NRI
Change from baseline in EASI score Percent change from baseline in EASI score	mITT population from originating combination therapy study -responders, partial responders	Descriptive using observed and mLOCF	Weeks 0-52	Exploratory Sensitivity for NRI	

Measure	Variable	Population ^a (Section 6.2.1)	Analysis Method ^b (Section 6.2.3)	Time Point	Analysis Type
		mITT population from originating combination therapy study -non responders	MMRM using observed Descriptive using mLOCF	Weeks 0-52	Exploratory Sensitivity for NRI
Eczema Area and Severity Index (EASI) ^c	Change from baseline in EASI score Percent change from baseline in EASI score	mITT population from open-label study	Descriptive using observed and mLOCF	Weeks 0-52	Exploratory
		Period 2 non-substudy population Open-label Period 2 non-substudy population	Descriptive using observed and mLOCF	Weeks 52-200	Exploratory
		Long term Baricitinib 4 mg population	Descriptive using observed and mLOCF	Weeks 52-200	Exploratory
		Randomized Downtitration Withdrawal Substudy Population Randomized Downtitration Withdrawal Substudy Population with Week 52 IGA of 0 or 1	ANCOVA using mLOCF	Week 52-200	Exploratory
Body Surface Area (BSA) Affected by AD	BSA Score Change from baseline in BSA Score	mITT population from originating combination therapy study - responders, partial responders	Descriptive using observed and mLOCF	Weeks 0-52	Exploratory
		mITT population from originating combination therapy study - nonresponders	MMRM using observed Descriptive using mLOCF	Weeks 0-52	Exploratory
		mITT population from open-label study	Descriptive using observed and MLOCF	Weeks 0-52	Exploratory
SCORing Atopic Dermatitis (SCORAD)	SCORAD score Change from baseline in SCORAD score Percent change from baseline in SCORAD score	mITT population from originating combination therapy study - responders, partial responders	Descriptive using observed and MLOCF	Weeks 0-52	Exploratory
		mITT population from originating combination therapy study - nonresponders	MMRM using observed Descriptive using mLOCF	Weeks 0-52	Exploratory

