6.11.3. Sensitivity Analyses

Sensitivity analyses are included to demonstrate robustness of analyses methods using different censoring rules, populations, and analyses assumptions. Sensitivity analyses for select outcomes have been previously described and include the following:

- analysis of select continuous outcomes with ANCOVA (Section 6.2.3), with missing data imputed using mLOCF (Section 6.4.3)
- analysis of select continuous outcomes in the randomized withdrawal and downtitration substudy using Week 52 as the baseline
- analysis of selected outcomes (IGA, EASI, ITCH-NRS), with missing data imputed using mLOCF

For analyses on and after the February 2021 DBL, NRI will be used as supportive sensitivity.

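### Period 2 absolute EASI change is measured from the originating-study baseline but adjusted only for the Week 52 EASI, which widens the substudy contrasts without biasing them

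*SAP*

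**What the plan says.** **Outcome.** SAP Section 6.2.2 (Period 2) states: "Baseline from originating study will also be used for EASI-related, continuous endpoints, such as EASI change or percent change from baseline". Section 6.2.4 (Derived Data) gives the matching formula: "change from baseline = postbaseline measurement at Visit x – baseline measurement from originating study". Other continuous endpoints are treated differently: "For the other continuous endpoints such as Itch NRS and DLQI change from baseline, the analysis will be done using the Week 52 baseline". Patients who enrolled directly through the open-label addendum have no originating study; their baseline is the last value on or before first study drug in JAHN.

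**Model.** Section 6.2.3 states: "Analysis of covariance will be the primary method of analysis for continuous efficacy and health outcome variables for Period 2". In that period the "ANCOVA model includes region, baseline disease severity at Week 52, treatment group, and baseline value at Week 52". Severity at Week 52 has two levels, IGA 0 or 1 and IGA 2. Nothing in the SAP adds the originating EASI to the Period 2 ANCOVA.

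**Contrast with Period 1.** There the covariate and the change score share a baseline. Section 6.3 states: "When an MMRM analysis is performed, baseline value from originating study and baseline-by-visit interactions will be included as covariates".

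**Where it applies.** Table JAHN.6.5 assigns "ANCOVA using mLOCF" to EASI change and percent change in the substudy population and labels the analysis exploratory. Section 6.11.3 also plans an "analysis of select continuous outcomes in the randomized withdrawal and downtitration substudy using Week 52 as the baseline", without naming the outcomes.

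**The concern.** For Itch NRS and DLQI in Period 2, the change score and the covariate both refer to Week 52. For EASI they refer to different times. The originating EASI is high and can vary widely: the addendum requires at least 16 at entry and says that its criteria match the feeder studies, and the scale runs to 72. Substudy patients have IGA 0 to 2 at Week 52, so their Week 52 EASI need not say much about where they started. Region and the Week 52 IGA stratum are not substitutes for the starting value.

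What is at stake is the width of the confidence intervals, and the power, for the withdrawal and downtitration contrasts on absolute EASI change. Section 6.2.3 says that these differences and their p-values serve for inference, and Section 6.1 makes no claim that the substudy is large enough to detect a difference.

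**Working it through.** The plan states no SD, effect or power for this analysis, so there is no figure to reproduce.

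**Formula.** Let Y be the Period 2 EASI that enters the model (after mLOCF), W the Week 52 EASI, B the originating EASI, and b the partial slope of Y on B given W.

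- SAP model, outcome Y − B adjusted for W: residual variance = Var(Y|W,B) + (1 − b)² × Var(B|W).
- With B added as a covariate: residual variance = Var(Y|W,B).
- Outcome Y − W adjusted for W: residual variance = Var(Y|W).

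The extra term vanishes only if b = 1, that is, if every extra point of originating EASI carries fully into Period 2 at a fixed Week 52 value.

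**Inputs.** From the documents: two-sided 0.05 (SAP 6.2), 1:1:1 rerandomization (5.2), about 600 substudy patients (6.1). Assumed: an even split over two entry doses and three arms, 600 / 6 = 100 per arm; SD(B) 8 to 13; SD(Y) 6 to 10; SD(W) 5; corr(B,W) 0.1 to 0.4; corr(B,Y) 0.1 to 0.5; corr(W,Y) 0.5; a true difference of 3 EASI points.

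**Central case:** SD(B) 10, SD(Y) 8, corr(B,W) 0.3, corr(B,Y) 0.3.

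- Var(B|W) = 100 × (1 − 0.09) = 91
- Var(Y|W) = 64 × (1 − 0.25) = 48, SD 6.93
- Cov(Y,B|W) = 10 × 8 × (0.3 − 0.3 × 0.5) = 12, so b = 12 / 91 = 0.13
- Var(Y|W,B) = 48 − 144 / 91 = 46.4, SD 6.81
- SAP model: 48 + 91 − 2 × 12 = 115, SD 10.72
- Variance ratio 115 / 46.4 = 2.48; SE ratio √2.48 = 1.57

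Power for 3 points is 51% under the SAP model and 88% with B added.

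**Ends of the grid**

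| SD(B) | SD(Y) | corr(B,W), corr(B,Y) | b | Variance, SAP model | Variance, B added | SE ratio |
|---|---|---|---|---|---|---|
| 8 | 10 | 0.4, 0.5 | 0.45 | 80.8 | 64.3 | 1.12 |
| 10 | 8 | 0.3, 0.3 | 0.13 | 115.0 | 46.4 | 1.57 |
| 13 | 6 | 0.1, 0.1 | 0.02 | 186.5 | 26.9 | 2.63 |

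**Simulation of the central case** (4,000 two-arm trials, 100 per arm, normal data, true difference 3.0)

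| Model | Mean estimate | Mean SE | Power |
|---|---|---|---|
| SAP: Y − B on W | 2.99 | 1.52 | 49% |
| Y − B on W and B | 2.99 | 0.97 | 87% |
| Y − W on W | 2.99 | 0.98 | 86% |

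All three recover the true difference. The two alternatives have nearly the same precision.

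**Percent change and responder endpoints.** The formula above does not carry over. In percent change B is a divisor, and separate simulations under assumed distributions put the gain between about nil and 1.13-fold. For EASI75 by logistic regression, power with and without B differed by no more than one percentage point, and in one check the SE of the treatment log odds rose slightly when B was added (ratio without to with B, 0.97 to 0.99).

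**The case against.** **The plan may already contain the remedy.** Since every other continuous endpoint uses Week 52 as its main Period 2 baseline, the Week 52 sensitivity analysis in Section 6.11.3 would differ from the main analysis only for EASI. Appendix 2 also listed substudy EASI against both baselines for the 4-month safety update. This is a reasonable inference about intent, but Section 6.11.3 does not name EASI, and Appendix 2 covers one lock. Neither alters the main Period 2 model.

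**The stakes are low.** This stands. The secondary substudy endpoints in Section 4.2 are IGA response, EASI75, time to retreatment and recapture of response; none is a continuous EASI change.

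**The change comes late.** This also stands. The Version 8 entry in the Revision History says that data to Week 104 are locked, and Section 4.3 makes later efficacy descriptive on observed data unless otherwise stated. A new covariate would mainly affect locked data.

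**There is a reason to keep the originating baseline.** Substudy entry requires IGA 0 to 2, so Week 52 EASI can be at or near zero, and percent change from it would be unstable or undefined. That argues against moving percent change to Week 52. It does not argue against adding a covariate for absolute change.

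**The size is assumed.** True. The direction is not in doubt unless b = 1, but a ratio of 2.6 needs a wide originating spread, a narrow Period 2 spread and weak correlation together.

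**Conclusion.** The point holds for absolute EASI change in the substudy. The model leaves avoidable originating-baseline variation in the error term, and the SE is about 1.1 to 2.6 times wider than necessary, centrally about 1.6. Those figures rest on assumed SDs and correlations; the mechanism rests on the SAP text.

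A reader might infer more, and the documents do not support it:

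- **Bias or false positives.** Treatment is rerandomized at Week 52, so leaving out a pre-treatment value does not shift the contrast or inflate the type I error.
- **Loss of the substudy's EASI evidence generally.** EASI75 is the secondary EASI endpoint and is analysed by a different model; continuous change is exploratory.
- **A similar loss for percent change.** The gain there is small to nil.
- **A need to alter the EASI50/75/90 logistic models.** The checks show almost no gain in power. The reported difference in percentages with its Newcombe-Wilson interval is not model-adjusted and would not move.

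This is a modest improvement worth making, not a flaw that threatens a main conclusion.

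**What to change.** In the Period 2 ANCOVA for absolute EASI change, add the EASI from before first study drug as a covariate beside the Week 52 value. This is the originating-study baseline, or the JAHN baseline for open-label addendum patients. The value is already needed to compute the outcome, so the cost is one model term and one degree of freedom.

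Alternatively, name absolute EASI change from Week 52 in the Section 6.11.3 sensitivity analyses. This gives nearly the same precision and needs only a wording change.

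For locks already completed, leave the prespecified result in place and report either version as a supplementary analysis, labelled as added after lock. Leave percent change and the EASI50/75/90 logistic models as they are.

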### **4.8. Statistical Considerations**

#### **4.8.1. Sample Size Determination**

This addendum will aim to enroll approximately 250 additional patients  $\geq 18$  years of age into the JAHN Study. It is anticipated that approximately 80% of enrolled patients will complete the first 52 weeks (treatment period 1). Of those, it is expected 30% will enroll into the JAHN randomized withdrawal and down-titration substudy. This addendum is descriptive in nature and the sample size is not based on any statistical power calculations.

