- **Screening and baseline period:** Screening should occur during the last visit of the originating study unless the patient received oral systemic AD treatment as rescue therapy during the originating study and needs additional time to complete the required 4-week washout period or the sponsor gave approval.
- **Treatment Period 1:** Treatment period from Week 0 to Week 52. Patients will be classified as responders, partial responders or nonresponders at the entry of Study JAHN based on the criteria given in Section 5.1.

- Treatment Period 2: Treatment period from Week 52 to 200 and will contain a randomized withdrawal and downtitration substudy. At Week 52, all patients will be evaluated for substudy eligibility, and the criteria are given in the Protocol. Patients not entered in the substudy will continue on their current treatment.
- Posttreatment follow-up period: Period from Week 200 (Visit 22) or Early Termination Visit (ETV) to approximately 28 days after the last dose of IP.

Abbreviations: BARI = baricitinib; IGA = Investigator’s Global Assessment; TCS = topical corticosteroids.

a Background TCS may be initiated or reinitiated at any time during the study, following the guidelines in the Protocol (Section 7.7.1) and will be provided as part of rescue or retreatment any time a patient’s IGA score becomes ≥ 3 as described in the Protocol (Sections 5.1.2.1 and 5.1.3.1).

b Eligible patients will be rerandomized in the withdrawal and downtitration substudy as described in the Protocol (Section 5.1.3.1). Patients who do not enroll in the substudy will remain on their treatment.

c Patients enrolled in the substudy will automatically be retreated if their IGA score becomes ≥ 3 as described in the Protocol (Section 5.1.3.1).

d Rescue is available as described in the Protocol (Section 5.1.2.1).

Figure JAHN.5.1. Illustration of study design for Clinical Protocol I4V-MC-JAHN.

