Patients on baricitinib 2 mg or baricitinib 4 mg who are considered nonresponders (IGA >2) at entry into Study JAHN may respond with continued baricitinib treatment. Time to first response (IGA of ≤ 1) will be assessed using cumulative incidence functions for patients remaining on the same dose from the originating study. This will be used to determine when continued baricitinib treatment is futile. Missing IGA data will be replaced using the NRI rule.

For the US submission DBL (data cut-off 13Dec2019), all patients originating from Studies JAHL or JAHM are expected to have either reached the Week 52 visit or have discontinued from the study. Fisher's exact test will be used to test for differences between each baricitinib dose (including those that are randomized to a different dose) and placebo in proportions of patients

experiencing AEs) discontinuation from study drug, and for other categorical safety data. Continuous vital signs, body weight, and other continuous safety variables, including laboratory variables will be analyzed by an ANCOVA with treatment group and baseline value in the model. The significance of within-treatment-group changes from baseline will be evaluated by testing whether or not the treatment group LSM changes from baseline are different from zero; the standard error for the LSM change will also be displayed. Differences in LSM will be displayed, with the p-value associated with the LSM comparison to placebo or appropriate comparator and a 95% CI on the LSM difference also provided. In addition to the LSMs for each group, the within-group p-value for the change from baseline will be displayed.

6.2.4. *Derived Data*

- age (year), derived using first dose date as the reference start date and July 1st of birth year and truncated to a whole-year (integer) age. Patients whose derived age is <18 will have the required minimum age of 18 at informed consent confirmed; reporting for age, age groups, and lab ranges, however, will be based on their derived age.
- age group (<65, ≥65 years old)
- age group (<65, ≥65 to <75, ≥75 to <85, ≥85 years old)
- body mass index (BMI) (kg/m^2) = $\text{Weight (kg)} / (\text{Height [cm]} / 100)^2$
- BMI category (<25 kg/m^2 , ≥25 to <30 kg/m^2 , ≥30 kg/m^2)
- the duration of AD from diagnosis (years) = $([\text{Date of informed consent} - \text{Date of AD diagnosis}] + 1) / 365.25$

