6.4. Handling of Dropouts or Missing Data

Intercurrent events (ICH E9 R1) are events which occur after randomization such that subsequent data (collected after the intercurrent event) are difficult to interpret.

Depending on the estimand being addressed, different methods will be used to handle missing data as a result of intercurrent events. Intercurrent events can occur through the following:

- application of the censoring rule (including after permanent study drug discontinuation or for responders and partial responders [on Placebo or baricitinib 1-mg] who are rescued to a higher dose [baricitinib 2 mg or baricitinib 4 mg])
- retreatment after downtitration or early withdrawal
- discontinuation
- missing an intermediate visit prior to discontinuation or rescue
- lost to follow-up

Noncensor intercurrent events are events that are not due to the application of any censoring rule (ie, the last 3 items in the list above).

Note that as efficacy and health outcome data can accrue after a patient permanently discontinues study drug or is rescued to either baricitinib 2 mg or baricitinib 4 mg (for responders and partial responders on placebo or baricitinib 1 mg), a censoring rule will be applied to all efficacy and health outcome observations subsequent to these events depending on the estimand being addressed.

The *Period 1 censoring rule* will censor efficacy after permanent study drug discontinuation or for responders and partial responders (on placebo or baricitinib 1 mg) who are rescued to a higher dose (baricitinib 2 mg or baricitinib 4 mg). This censoring rule will be applied to all efficacy endpoints conducted for the responder, partial responder, and nonresponder mITT populations (defined in Section 6.2.1). For responders and partial responders, the censoring rule will censor efficacy data after permanent study drug discontinuation or rescue date, whichever occurs first. For nonresponders, the censoring rule will censor efficacy data after permanent study drug discontinuation.

The *Period 2 censoring rule* will censor efficacy data after permanent study drug discontinuation or after retreatment, whichever occurs first. This censoring rule will be applied to efficacy endpoints and safety conducted for the Period 2 population corresponding to the withdrawal and downtitration substudy.

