6.4.1. Nonresponder Imputation

An NRI method imputes missing values as nonresponses and can be justified based on the composite strategy for handling intercurrent events (ICH E9 R1). This imputation procedure assumes the effects of treatment disappear after an occurrence of the intercurrent event (described in Section 6.4). For analyses which utilize censoring, randomized patients without at least 1 postbaseline observation will be defined as nonresponders for all visits. As well, patients who are missing a value prior to discontinuation or were rescued to a higher dose (if censoring on the latter) (ie, the patient is missing an intermediate visit) will be imputed as nonresponders on that visit only.

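### The futility reading in SAP 6.2.3 rests on a cumulative incidence curve whose slope can fall while the chance of response among patients still treated is unchanged

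*SAP*

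**What the plan says.** SAP Section 6.2.3 observes that patients on 2 mg or 4 mg who enter as nonresponders "may respond with continued baricitinib treatment". Time to first IGA ≤1 "will be assessed using cumulative incidence functions for patients remaining on the same dose from the originating study". The stated purpose is a decision: "This will be used to determine when continued baricitinib treatment is futile". For gaps in the data, "Missing IGA data will be replaced using the NRI rule".

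Two other sections determine how discontinuation enters the curve. Section 6.4: "For nonresponders, the censoring rule will censor efficacy data after permanent study drug discontinuation". Section 6.4.1, on NRI: "This imputation procedure assumes the effects of treatment disappear after an occurrence of the intercurrent event". Together they make a patient who stops drug before responding a nonresponder at every later visit.

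For this curve the SAP gives no futility threshold, time window, number at risk, confidence interval, competing event, or probability of later response among patients still on drug. Time to first response has no row in Table JAHN.6.4 or JAHN.6.5.

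**The concern.** Whether continuing is worthwhile at time t depends on the chance of a later response among patients who at t are still on drug and have not yet responded. The cumulative incidence curve answers another question: what fraction of all who entered have responded by t. Its slope is the product of the response rate among those still eligible and the share of the cohort still eligible. The second factor falls throughout follow-up, for two reasons.

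- Responders leave the group that can have a first response. This happens with or without dropout.
- Discontinued patients can add no response but, under NRI, remain in the denominator. This adds to the flattening.

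Reading futility from the shape of the curve thus mixes a falling chance of response, which is relevant, with a shrinking eligible group, which is not. With no criterion written down, the call is left to visual judgement of a slope that declines anyway.

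**Working it through.** The documents state no figure for this analysis, so there is nothing to reproduce.

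**Inputs**
- Follow-up is 52 weeks, or 13 blocks of 4 weeks (SAP Section 5.1: "Treatment period from Week 0 to Week 52").
- Response hazard hr: not given. Assumed constant at 0.05 per 4 weeks, with 0.03 as an alternative.
- Dropout D by Week 52 in the absence of response: not given for this group. The only figure concerns the open-label addendum (Protocol Section 4.8.1: "It is anticipated that approximately 80% of enrolled patients will complete the first 52 weeks"), i.e. 20% not completing. Assumed range: 0%, 20%, 30% and about 48%. The last corresponds to a hazard of 0.05, since 1 − exp(−0.65) = 0.478.

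**Formulas** (t in weeks, hazards per 4 weeks)
- hd = −ln(1 − D)/13
- CIF(t) = hr/(hr + hd) × [1 − exp(−(hr + hd)t/4)]
- Share still treated and unresponsive at Week 36: S = exp(−9(hr + hd))
- Conditional 16-week chance at Week 36 = [CIF(52) − CIF(36)]/S

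Algebraically, CIF(52) − CIF(36) = S × CIF(16). The late gain is therefore the early gain multiplied by S, and the conditional chance equals CIF(16) exactly.

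**Worked case, D = 20%.** hd = 0.2231/13 = 0.0172, so the total hazard is 0.0672. CIF(16) = 0.744 × (1 − exp(−0.2687)) = 17.5%. S = exp(−0.6045) = 0.546. Late gain = 0.546 × 17.5 = 9.6 points, a fall of 1 − 0.546 = 45%. Conditional chance = 9.6/0.546 = 17.5%.

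**All cases, hr = 0.05**

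| D by Week 52 | Gain Weeks 0-16 (points) | Gain Weeks 36-52 (points) | Fall | S at Week 36 | Conditional chance at Week 36 |
|---|---|---|---|---|---|
| 0% | 18.1 | 11.6 | 36% | 0.638 | 18.1% |
| 20% | 17.5 | 9.6 | 45% | 0.546 | 17.5% |
| 30% | 17.2 | 8.6 | 50% | 0.498 | 17.2% |
| about 48% | 16.5 | 6.7 | 59% | 0.407 | 16.5% |

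With hr = 0.03, S is 0.763, 0.654, 0.596 and 0.487, so the falls are 24%, 35%, 40% and 51%. In the last case the late gain is 5.0 points against a conditional 10.3%.

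**Second check, discrete time.** Let h be a constant chance of first response per 4-week block, with constant dropout d = 1 − (1 − D)^(1/13). The step in block k is h[(1 − h)(1 − d)]^(k−1). For h of 2% to 6% and D of 0% to 40%, the last step is 0.78 to 0.30 of the first: 22% to 70% of the slope is lost with no change in h. For h = 4% and D = 30%, steps fall from 4.00 to 1.76 points. Responders leaving accounts for a fall to 2.45, and dropout under NRI for the rest. A simulation of 400,000 patients in that case gave a flat 4.0% to 4.1% per 4 weeks among those still treated.

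**Can a reader recover the answer from the curve?** Not under NRI. Dividing each step by one minus the curve leaves dropouts in the denominator. At h = 4%, the last block then appears as 3.10%, 2.67% or 2.25% for D of 20%, 30% or 40%.

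**The case against.** Several points on the other side are sound.

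- **Flattening is a property of any cumulative proportion.** It is not a defect of NRI. With hr = 0.05, a 36% fall occurs with no dropout at all, so NRI is an added contributor, not the cause.
- **The largest figure needs heavy dropout.** The 59% fall assumes about 48% discontinuing. At the addendum's 20% it is 45%. A reader might infer that dropout is high among entry nonresponders; the documents do not say so.
- **No plateau is shown.** Under a constant hazard the slope never reaches zero, and the SAP does not say that a plateau or slope is the criterion. A reader might infer that the curve will produce a wrong futility call, but that depends on a cut-off the SAP does not give. If the chance of response does decline over time, part of the flattening is real.
- **Consequence is limited.** Time to first response is not among the listed objectives. No section ties the curve to advice on stopping treatment, so premature stopping advice is conjecture.
- **Related output exists.** Section 6.7 gives disposition through Weeks 16, 36 and 52 for nonresponders, and Table JAHN.6.5 gives IGA response over Weeks 0-52 under NRI and mLOCF for nonresponders from the combination study.

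The related output does not close the gap, because none of it is a probability conditional on being treated and unresponsive. Nor does the move to mLOCF from February 2021: before a first response the value carried forward is itself a nonresponse, so first-response times do not change. Treating discontinuation as a competing event gives the same denominator as NRI. Section 6.17's statement that the study will not stop for futility concerns the trial, not how long a patient continues.

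**Conclusion.** The point holds as a mismatch between tool and stated use. The curve is a valid estimate of the cumulative proportion responding on treatment. Its shape does not identify when continued treatment stops being worthwhile, and the plan supplies neither the conditional quantity nor a criterion.

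For hr = 0.05 the apparent decline between the first and last 16 weeks is 36% to 59% across the dropout range shown, and 45% at the only dropout figure in the documents, with no true decline in any case. These sizes rest on assumed constant hazards and on dropout independent of response. The direction does not depend on the exact rates, because the eligible share of the cohort falls whatever they are.

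The documents support saying that a false futility reading is possible. They do not support saying that it will occur, that dropout in this group is high, or that treatment advice would follow. This is a cheap improvement and does not threaten the primary analysis.

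**What to change.** - Keep the cumulative incidence curve as description. Show discontinuation as a competing event, with numbers at risk under the plot.
- Base any futility statement on a landmark table. At each scheduled visit, give the number still on the same dose without a response, and the proportion (95% CI) first reaching IGA ≤1 within the next 16 weeks and by Week 52.
- State that discontinuation after the landmark counts as nonresponse, and give a version that censors it as sensitivity. The two differ: with hr = 0.05 and about 48% dropout, the 16-week chance is 16.5% counting discontinuation as failure and 1 − exp(−0.20) = 18.1% censoring it.
- Where 16 weeks after a landmark is not a scheduled visit, use the last scheduled visit inside the window. Truncate at Week 52, when patients may be rerandomized.

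The cost is one table from data already collected. Intervals will be wide at late landmarks, which is itself worth showing. SAP Version 8 records that data to Week 104 are already locked, so the table must be labelled post hoc for Period 1. No clinical stopping rule is proposed here.
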